Appendix 3 Tables, Figures, Listings, and Supportive SAS Output Appendices

The TFL shells for this study are provided in a separate document titled "Gan & Lee GL-GLAT2-3002 TFL Shells Version 3.0.docm," which includes a complete table of contents listing all required outputs.

Gan & Lee Pharmaceuticals USA

PRAHEALTHSCIENCES

Sponsor: Gan & Lee Pharmaceuticals, USA Corporation
Protocol no: GL-GLAT2-3002

Statistical Analysis Plan
Version Date: 16-Nov-2020

Appendix 4 Immunogenic- and Efficacy-Interfering Important Protocol Deviations

Type of Deviation/ Code	Deviation Description	Important protocol deviation	Sub-Category	PD Effect on Immunogenicity	PD Effect on Efficacy
1. INCLUSION CRITERIA	Any deviation from inclusion criteria after the ICF has been signed				
1. INCLUSION CRITERIA n. 1	Enrollment of a male or a nonpregnant, nonlactating female not between the ages of 18 and 75 years, inclusive.	Yes	1	No	No
1. INCLUSION CRITERIA n. 2	Enrollment of a subject unable to provide written, personally signed, and dated informed consent before initiating any study-related procedures.	Yes	2	No	No
1. INCLUSION CRITERIA n. 3	Enrollment of a subject unable to understand and fully comply with all study procedures and restrictions.	Yes	3	No	No
1. INCLUSION CRITERIA n. 4	Enrollment of a subject, insulin-naive, with a confirmed diagnosis of type 2 diabetes mellitus who has not been on at least 2 approved OAMs for at least 12 weeks before screening.	Yes	4.1	Yes	Yes
1. INCLUSION CRITERIA n. 4	Enrollment of a subject, who is treated with a basal insulin, with a confirmed diagnosis of type 2 diabetes mellitus who has not been treated with insulin for at least 6 months or has not been on at least 1 approved OAM or the type or brand of insulin has changed within 6 months prior to screening.	Yes	4.2	Yes	Yes
1. INCLUSION CRITERIA n. 5	Enrollment of an insulin-naive subject with HbA1c > 11.0%.	Yes	5.1	No	Yes
1. INCLUSION CRITERIA n. 5	Enrollment of a subject previously on a basal insulin regimen with HbA1c < 7.0% or > 11.0%.	Yes	5.2	No	Yes
1. INCLUSION CRITERIA n. 6	Enrollment of subjects with body mass index (BMI) < 19 kg/m ² or > 35 kg/m ² .	Yes	6	Yes	Yes
1. INCLUSION CRITERIA n. 7	Enrollment of a subject unable to adhere to a prudent diet and exercise regimen recommended by the medical provider, and not willing to maintain these consistently for the duration of the study.	Yes	7	Yes	Yes
1. INCLUSION CRITERIA n. 8	Enrollment of a subject who had taken concomitant thyroid medications without having a stable dosage for 90 days before screening.	Yes	8	Yes	Yes

Gan & Lee Pharmaceuticals USA

PRAHEALTHSCIENCES

Sponsor: Gan & Lee Pharmaceuticals, USA Corporation
Protocol no: GL-GLAT2-3002

Statistical Analysis Plan
Version Date: 16-Nov-2020

Type of Deviation/ Code	Deviation Description	Important protocol deviation	Sub-Category	PD Effect on Immunogenicity	PD Effect on Efficacy
2. EXCLUSION CRITERIA	Any deviation from exclusion criteria after the ICF has been signed	Yes			
2. EXCLUSION CRITERIA n. 1	Enrollment of a subject who participated in another clinical study or use of any study drug within 30 days before screening.	Yes	1	Yes	Yes
2. EXCLUSION CRITERIA n. 2	Enrollment of subject with previous use of a biosimilar insulin, either basal or bolus.	Yes	2	Yes	Yes
2. EXCLUSION CRITERIA n. 3	Enrollment of subject with diabetic ketoacidosis within a year before screening.	Yes	3	No	No
2. EXCLUSION CRITERIA n. 4	Enrollment of a subject with a history of brittle type 2 diabetes mellitus within the year before screening (e.g., multiple hospitalizations related to diabetes mellitus and/or severe hypoglycemia for which the subject required 3rd party assistance).	Yes	4	Yes	Yes
2. EXCLUSION CRITERIA n. 5	Enrollment of a subject with any severe, delayed sequela of diabetes mellitus, e.g., worsening end-stage renal disease, advanced coronary artery disease, or myocardial infarction within the year before screening, or autonomic peristaltic problems, e.g., gastroparesis.	Yes	5	Yes	Yes
2. EXCLUSION CRITERIA n. 6	Enrollment of a subject with anticipated change in insulin used during the study.	Yes	6	Yes	Yes
2. EXCLUSION CRITERIA n. 7	Enrollment of a subject without obtaining TSH and T4 results before randomization and both TSH and T4 results are within normal ranges measured by the central laboratory after randomization (during the treatment period).	Yes	7.1	No	No
2. EXCLUSION CRITERIA n. 7	Enrollment of a subject without obtaining TSH and T4 results before randomization and TSH and/or T4 results are not available or out of normal ranges after randomization (during the treatment period).	Yes	7.2	Yes	Yes
2. EXCLUSION CRITERIA n. 8	Enrollment of a subject with BMI < 19 kg/m2 or > 35 kg/m2.	Yes	8	Yes	Yes
2. EXCLUSION CRITERIA n. 9	Enrollment of a subject without obtaining hematology or chemistry tests or any clinically significant (in the opinion of the Investigator) hematology or chemistry test results at	Yes	9	Yes	Yes

Gan & Lee Pharmaceuticals USA

PRAHEALTHSCIENCES

Sponsor: Gan & Lee Pharmaceuticals, USA Corporation
Protocol no: GL-GLAT2-3002

Statistical Analysis Plan
Version Date: 16-Nov-2020

Type of Deviation/ Code	Deviation Description	Important protocol deviation	Sub-Category	PD Effect on Immunogenicity	PD Effect on Efficacy
	screening, including any liver function test > 3 x the upper limit of normal.				
2. EXCLUSION CRITERIA n. 10	Enrollment of a subject with documented anti-insulin antibodies in the past.	Yes	10	Yes	Yes
2. EXCLUSION CRITERIA n. 11	Enrollment of a subject treated with glucocorticosteroids (newly prescribed or high dose), immunosuppressants, or cytostatic agents within 60 days before screening, or treated with a prohibited medication up to randomization.	Yes	11	Yes	Yes
2. EXCLUSION CRITERIA n. 12	Enrollment of a subject using medication intended to cause weight loss or weight gain during the screening.	Yes	12	Yes	Yes
2. EXCLUSION CRITERIA n. 13	Enrollment of a subject with a history of alcohol or substance use disorder within the 2 years before screening.	Yes	13	No	No
2. EXCLUSION CRITERIA n. 14	Enrollment of a subject with any history of previous or anticipated treatment with interferons.	Yes	14	Yes	Yes
2. EXCLUSION CRITERIA n. 15	Enrollment of a subject with any history of malignant disease within 5 years before screening, except for adequately treated basal cell carcinoma.	Yes	15	Yes	Yes
2. EXCLUSION CRITERIA n. 16	Enrollment of a subject with a severe concomitant physical or psychiatric diseases or conditions.	Yes	16	No	No
2. EXCLUSION CRITERIA n. 17	Enrollment of a subject with a history of a positive test result for HIV, hepatitis B, or hepatitis C.	Yes	17	Yes	Yes
2. EXCLUSION CRITERIA n. 18	Enrollment of a subject with any history of pancreatitis or pancreatotomy.	Yes	18	Yes	Yes
2. EXCLUSION CRITERIA n. 19	Enrollment of a subject with any diagnosis or condition that requires the subject to undergo procedures that could decrease antibodies in plasma or that would require treatment with immunosuppressant agents.	Yes	19	Yes	Yes
2. EXCLUSION CRITERIA n. 20	Enrollment of a subject with any condition e.g., splenectomy, autoimmune disease, or rheumatologic disease, that could affect immunologic responses, could indicate an altered immune system, or could require	Yes	20	Yes	Yes

Gan & Lee Pharmaceuticals USA

PRA HEALTH SCIENCES

 Sponsor: Gan & Lee Pharmaceuticals, USA Corporation
 Protocol no: GL-GLAT2-3002

 Statistical Analysis Plan
 Version Date: 16-Nov-2020

Type of Deviation/ Code	Deviation Description	Important protocol deviation	Sub-Category	PD Effect on Immunogenicity	PD Effect on Efficacy
	treatment with a prohibited concomitant medication.				
2. EXCLUSION CRITERIA n. 21	Enrollment of a subject with any unresolved infection or a history of active infection within 30 days before screening other than mild or viral illness (as judged by the investigator).	Yes	21	Yes	Yes
2. EXCLUSION CRITERIA n. 22	Enrollment of a subject with any disease or condition that in the opinion of the Investigator could confound the study results or limit the subject's ability to participate in the study or comply with follow-up procedures; or any other factor that would indicate a significant risk of loss to follow up.	Yes	22	Yes	Yes
2. EXCLUSION CRITERIA n. 23	Enrollment of a subject with intolerance or history of hypersensitivity to insulin glargine or any excipient of IP.	Yes	23	Yes	Yes
2. EXCLUSION CRITERIA n. 24	Enrollment of a subject unable or unwilling to wear the CGM sensor as required for the study, or to comply with the concomitant medication requirements in the FreeStyle Libre Pro Indications and Important Safety Information, during the CGM periods.	Yes	24	No	No
3. STUDY DRUG	Deviations related to study drug				
3. STUDY DRUG	A single dose of study drug is not administered by the subject due to reason(s) other than safety in any given 2-week span during treatment period.	No	1	No	No
3. STUDY DRUG	More than one dose of study drug is not administered by the subject due to reason(s) other than safety in any given 2-week span during treatment period.	Yes	2	No	Yes
3. STUDY DRUG	Subject received the study drug that was assigned to another subject, which is consistent with their assigned treatment.	No	3	No	No
3. STUDY DRUG	Subject received the study drug that was assigned to another subject, which is different than their assigned treatment.	Yes	4	Yes	Yes
3. STUDY DRUG	Subject failed to return the study drug.	No	5	No	No

Gan & Lee Pharmaceuticals USA PRAHEALTHSCIENCES

Sponsor: Gan & Lee Pharmaceuticals, USA Corporation
Protocol no: GL-GLAT2-3002

Statistical Analysis Plan
Version Date: 16-Nov-2020

Type of Deviation/ Code	Deviation Description	Important protocol deviation	Sub-Category	PD Effect on Immunogenicity	PD Effect on Efficacy
3. STUDY DRUG	Failure to adjust doses of the study drug according to the instructions provided by the Investigator (especially where doses are expected to have a major impact on outcome) during the treatment period or failure to adjust the previously prescribed basal insulin during the Dose Optimization period.	Yes	6	No	Yes
3. STUDY DRUG	BID dosing of the study drug.	No	7	No	No
3. STUDY DRUG	GCP compliance - Drug Accountability not properly documented by site staff.	No	8	No	No
3. STUDY DRUG	A temperature excursion occurred and the proper notification, quarantine and release processes were not followed. The study drug in question was not administered to subjects.	No	9	No	No
3. STUDY DRUG	A temperature excursion occurred and the proper notification, quarantine and release processes were not followed. The study drug in question was administered to subjects without documentation of its stability.	Yes	10	Yes	Yes
3. STUDY DRUG	Mishandling, potential theft, loss of study drug at the site.	No	11	No	No
3. STUDY DRUG	Consistent or repeated failure by subject to document drug administration in the Mealtime and Insulin Dose Record Card during the CGM wearing period.	No	12	No	No
3. STUDY DRUG	Any deviation not covered by current Protocol Deviation Guidance codes related to the study drug.	TBD	13	TBD	TBD
4. ASSESSMENT - SAFETY	Failure to complete any safety assessments at study visits.				
4. ASSESSMENT - SAFETY	Protocol-defined baseline evaluations not performed before institution of the study drug.	Yes	1	No	No
4. ASSESSMENT - SAFETY	Failure to take action in response to apparent Hypoglycemia and failure to appropriately monitor the subject.	Yes	2	No	No
4. ASSESSMENT - SAFETY	Failure to report Serious Adverse Event (SAE) to the IRB/IEC or Sponsor within 24 hrs of knowledge of event.	Yes	3	No	No
4. ASSESSMENT - SAFETY	A failure to complete a single or multiple safety assessments (urinalysis, pregnancy test, vital signs, body weight) at two consecutive visits.	Yes	4	No	No

Gan & Lee Pharmaceuticals USA PRAHEALTHSCIENCES

Sponsor: Gan & Lee Pharmaceuticals, USA Corporation
Protocol no: GL-GLATZ-3002

Statistical Analysis Plan
Version Date: 16-Nov-2020

Type of Deviation/ Code	Deviation Description	Important protocol deviation	Sub-Category	PD Effect on Immunogenicity	PD Effect on Efficacy
4. ASSESSMENT - SAFETY	A failure to complete a single safety assessment (hematology, chemistry, thyroid labs, urinalysis, pregnancy test, vital signs, body weight) at a single visit.	No	5	No	No
4. ASSESSMENT - SAFETY	Performing additional study procedures (not listed in the protocol schedule of procedures and assessments except for unscheduled visits done for safety reasons) without approval of Sponsor and IRB/EC.	Yes	6	No	No
4. ASSESSMENT - SAFETY	Failure to complete single or multiple safety assessments (hematology, chemistry, thyroid labs, urinalysis, pregnancy test, vital signs, body weight, ECG, PE) at the final or Early Termination (ET) visit.	Yes	7	No	No
4. ASSESSMENT - SAFETY	AEs not assessed at a study visit (excluding hypoglycemia and not clinically significant hyperglycemia).	Yes	8	No	No
4. ASSESSMENT - SAFETY	Subject becomes pregnant during the study and is not withdrawn from the study.	Yes	9	No	No
4. ASSESSMENT - SAFETY	Partner of a male subject becomes pregnant during the study and pregnancy not reported.	Yes	10	No	No
4. ASSESSMENT - SAFETY	Failure to repeat laboratory tests for unexplained abnormal laboratory test results.	No	11	No	No
4. ASSESSMENT - SAFETY	A failure to complete multiple safety assessments (hematology, chemistry, thyroid labs, urinalysis, pregnancy test, vital signs, body weight) at a single visit.	Yes	12	No	No
4. ASSESSMENT - SAFETY	Failure to complete urine pregnancy test for all women of childbearing potential at study visit(s) and confirmed pregnancy later.	Yes	13	No	No
4. Assessment - Safety	Failure to follow the protocol (or any safety related plans) such that the safety of the subject or other subjects in the study is significantly impacted.	Yes	14	No	No
5. ASSESSMENT - EFFICACY	Failure to complete any efficacy assessments at study visits.				
5. ASSESSMENT - EFFICACY	Failure to complete HbA1c and/or Fasting Blood Glucose sampling at two consecutive visits, or at Baseline (Screening or Day 1), or at V9/Early Termination.	Yes	1	No	Yes
5. ASSESSMENT - EFFICACY	Failure to complete HbA1c and/or Fasting Blood Glucose sampling at a visit other than at	No	2	No	No

Gan & Lee Pharmaceuticals USA

PRAHEALTHSCIENCES

Sponsor: Gan & Lee Pharmaceuticals, USA Corporation
Protocol no: GL-GLAT2-3002

Statistical Analysis Plan
Version Date: 16-Nov-2020

Type of Deviation/ Code	Deviation Description	Important protocol deviation	Sub-Category	PD Effect on Immunogenicity	PD Effect on Efficacy
	Baseline (Screening or Day 1), or at V9/Early Termination.				
6. VISIT WINDOW	Whole visit missed or out of visit window.				
6. VISIT WINDOW	Missing an entire visit	No	1	No	No
6. VISIT WINDOW	Visit or procedure out of window	No	2	No	No
7. INFORMED CONSENT (ICF)	ICF process not conducted per ICH/GCP Guidelines or CFR.				
7. INFORMED CONSENT (ICF)	Subject signed a version of the ICF that is not approved by IRB/IEC.	Yes	1	No	No
7. INFORMED CONSENT (ICF)	Failure to obtain informed consent (or amended ICF), or Informed consent (or amended ICF) obtained after initiation of study procedures. Either missing subject signatures or missing designated caregiver's signatures (if subject cannot sign) on the consent form.	Yes	2	No	No
7. INFORMED CONSENT (ICF)	Missing original signed and dated consent form (only a photocopy available) or inappropriate documentation of informed consent, such as missing signatures (other than the subject's or designated caregiver's).	Yes	3	No	No
7. INFORMED CONSENT (ICF)	Use of an invalid, or outdated consent form.	Yes	4	No	No
7. INFORMED CONSENT (ICF)	Inadequate documentation of the informed consent process in subject source documents.	Yes	5	No	No
8. SAMPLE MANAGEMENT - HbA1c	Site does not manage the HbA1c sample per laboratory manual				
8. SAMPLE MANAGEMENT - HbA1c	HbA1c sample not managed according to Laboratory Manual (e.g. shipment timelines are not followed however sample storage and stability of the sample are not impacted).	No	1	No	No
9. SAMPLE MANAGEMENT - A1A/NAB	Site does not manage the A1A/NAB sample per protocol and/or pre laboratory manual				
9. SAMPLE MANAGEMENT - A1A/NAB	Any A1A/NAB samples not collected at protocol defined visits.	Yes	1	No	No
9. SAMPLE MANAGEMENT - A1A/NAB	Any A1A/NAB samples not collected pre-dose during the protocol defined visits.	No	2	No	No
9. SAMPLE MANAGEMENT - A1A/NAB	Any A1A/NAB samples not managed according to Laboratory Manual (e.g. shipment timelines are not followed however, sample storage and stability of the samples are not impacted).	No	3	No	No
9. SAMPLE MANAGEMENT - A1A/NAB	Storage temperature of A1A/NAB samples not managed according to Laboratory Manual.	Yes	4	Yes	No

Gan & Lee Pharmaceuticals USA PRAHEALTHSCIENCES

Sponsor: Gan & Lee Pharmaceuticals, USA Corporation
Protocol no: GL-GLAT2-3002

Statistical Analysis Plan
Version Date: 16-Nov-2020

Type of Deviation/ Code	Deviation Description	Important protocol deviation	Sub-Category	PD Effect on Immunogenicity	PD Effect on Efficacy
10. PROHIBITED CON-MEDS	Use of prohibited Concomitant-Medication (Con-Meds)				
10. PROHIBITED CON-MEDS	Received a prohibited concomitant medication according to protocol after randomization (during the treatment period).	Yes	1	Yes	Yes
11. Continuous Glucose Monitor (CGM) DEVICE	Continuous Glucose Monitor (CGM) issues				
11. CGM DEVICE	Repeated or consistent failure of the subject to return the CGM device.	No	1	No	No
11. CGM DEVICE	Repeat or persistent failure of the subject to complete and return the 8-day Mealtime & Insulin Dose Record.	No	2	No	No
11. CGM DEVICE	Failure by the site to apply the CGM sensor at the appropriate study timepoint.	No	3	No	No
12. UNDOCUMENTED HYPOGLYCEMIC EVENT RECORD	Hypoglycemic Event reporting issue				
12. UNDOCUMENTED HYPOGLYCEMIC EVENT RECORD	Failure to report a hypoglycemic event.	Yes	1	No	No
12. UNDOCUMENTED HYPOGLYCEMIC EVENT RECORD	Hypoglycemic event reported, but not in a timely manner.	No	2	No	No
13. OTHER	Others Not Included in the above mentioned categories				
13. OTHER	Failure to comply with requirements of the IRB for documentation and necessary notification.	Yes	1	No	No
13. OTHER	Any deviation not covered by current Protocol Deviation Guidance codes.	TBD	2	No	No
13. OTHER	The number of subjects enrolled by a site is over a pre-approved site enrollment limit without permission.	No	3	No	No
13. OTHER	Subject not registered in IXRS prior to initiation of the study treatment.	Yes	4	No	No
13. OTHER	Any repeated inconsistency of source documents and eCRF (e.g. Date of birth, etc.).	Yes	5	No	No
13. OTHER	Amended ICF signed at a later visit but no new procedures as per the amended Protocol were implemented before the signature.	No	6	No	No

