### 8.4.1 Inclusion Criteria

Subjects must satisfy all of the following entry criteria before they will be allowed to participate in the study:

1. Male or nonpregnant, nonlactating female subjects between the ages of 18 and 75 years, inclusive
2. Ability to provide written, personally signed, and dated informed consent to participate in the study, in accordance with the ICH GCP Guideline E6 and all applicable regulations, before initiating any study-related procedures
3. Ability to understand and fully comply with all study procedures and restrictions.
4. Subjects with a confirmed diagnosis of type 2 diabetes mellitus who meet one of the following:
  - a. If insulin-naïve, subjects should have been on at least 2 approved OAMs for at least 12 weeks before screening, and the clinician has decided to add insulin therapy
  - b. If already being treated with a basal insulin, subjects should have been treated with insulin for at least 6 months in addition to at least 1 approved OAM, and must not have changed the type or brand of insulin within 6 months prior to screening
5. HbA1c values as follows:
  - a. If insulin-naïve, HbA1c ≤ 11.0%
  - b. If previously on a basal insulin regimen, HbA1c ≥ 7.0% and ≤ 11.0%
6. Body mass index (BMI) ≤ 45 kg/m^2
7. Adherence to a prudent diet and exercise regimen recommended by the medical provider, and willingness to maintain these consistently for the duration of the study

8. Concomitant medications are allowed, provided that no significant dosing changes are anticipated during the study (see the exclusion criteria below and [Appendix 3 \[Section 17.3\]](#) for specific allowed and prohibited concomitant medications); for concomitant thyroid medications, subjects must have been on a stable dosage for 90 days before screening

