This SAP should be read in conjunction with the study protocol and case report forms (CRF). This version of the plan has been developed using the protocol amendment 3 dated 25APR2019 and CRF dated 15-Apr-2019. Any further changes to the protocol or CRF may necessitate updates to the SAP.

The study is an open-label study, investigators and subjects are not blinded. However, to avoid the introduction of operational bias into final study results and to increase the interpretability and reliability of the data, certain roles of the Sponsor and study team will be blinded. Details will be provided in the Data Blinding and Documentation of Aggregate Data Dissemination Plan. A final version of the SAP will be issued for sponsor approval prior to database lock, at which point the blinded team members will become unblinded to the actual randomization codes in aggregate form.

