3.1 Changes from Protocol

Per FDA comment, Wald method has been replaced with logistic regression approach to calculate the difference in proportions along with the corresponding 90% CI for the primary endpoint and corresponding sensitivity analyses. The delta method will be used to calculate the standard error for the difference and the associated confidence interval.

Also, per FDA suggestion, separately in each treatment group, the imputation will use outcomes in patients who discontinued treatment but provided a visit Week 26 glycosylated hemoglobin (HbA1c) measurement if sufficient data are available to impute outcomes in patients without actual visit Week 26 recorded results, under the assumption of missing not at random (MNAR). Full details are provided in Section 11.7 below.

4. Study Objectives

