7.1 General

1) Actual Treatment

The actual treatment received is defined as the IP treatment the subject received during the study, regardless of the treatment the subject was allocated to by randomization. If a subject receives both Gan & Lee Insulin Glargine Injection and Lantus® during the study period for whatever reason, then the actual treatment will be based on the treatment taken on the majority of days during the study.

2) Assessment after EOT

Assessment after EOT is defined as AIA/HbA1c assessment documented after date of EOT visit. If date of EOT visit is missing it is defined as assessment documented after date of last dose of IP + 1 day (to consider assessments of subjects who perform the visit assessment before daily dose of IP).

3) Average Daily Dose of IP

Average Daily Dose is defined as captured on the Average Daily Dose of Study Drug CRF page.

4) Baseline

For each endpoint of interest, unless otherwise noted, the study baseline is defined as the last non-missing assessment taken prior to or on the date of the first dose of study IP. For subjects whose treatment assignment is randomly assigned but not dosed after the randomization visit, the baseline is defined as the last non-missing assessment prior to or on the date of randomization.

5) Change from Baseline

Change from baseline is defined as (value at post-baseline visit – value at baseline).

6) Completer Week 26

A subject is defined as a Completer Week 26 if the answer to the question "Did the subject complete the study?" is "Yes" on the End of Study CRF page and who received IP for at least 22 weeks.

7) Dates of First and Last Dose

The date of first dose of IP is defined as the date of first dose of IP documented on the First Dose of Study IP CRF page and the date of last dose of IP is defined as the date of last dose of IP documented on the End of Study 2 CRF page. If no date of first dose of IP is available, the date of randomization will be selected as the date of first dose of IP. If no date of last dose of IP is available, the date of completion/discontinuation documented on the End of Study CRF page will be selected as the date of last dose. If date of last dose of IP is not available and subject is lost to follow up based on End of Study CRF page, date of last scheduled visit or date of last telephone contact where an average daily dose is recorded, will be used as the date of last dose of IP.

8) Diabetes Disease Duration

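### SAP Appendix 4 codes BMI below 19 or above 35 kg/m² as an important eligibility deviation, Protocol Amendment 3 admits BMI up to 45 with no lower limit, and neither document says which protocol version governs the coding

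*SAP*

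**What the plan says.** **Protocol Amendment 3.** Inclusion criterion 6 in section 8.4.1 reads "Body mass index (BMI) ≤ 45" kg/m², and exclusion criterion 8 in section 8.4.2 excludes values above 45. The synopsis agrees. No lower limit appears anywhere.

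**SAP Appendix 4.** The row for inclusion criterion 6 begins "Enrollment of subjects with body mass index (BMI) < 19" and goes on to values above 35 kg/m². The row for exclusion criterion 8 is "Enrollment of a subject with BMI < 19 kg/m2 or > 35 kg/m2". Both rows are marked Yes for important deviation, Yes for effect on immunogenicity and Yes for effect on efficacy. The block headers are "Any deviation from inclusion criteria after the ICF has been signed" and "Any deviation from exclusion criteria after the ICF has been signed"; neither names a protocol version.

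**SAP basis.** The Introduction states: "This version of the plan has been developed using the protocol amendment 3 dated 25APR2019". Section 3.1 lists changes from the protocol, such as "Per FDA comment, Wald method has been replaced with logistic regression approach", and no change to BMI.

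**How the rows are used.** SAP 11.3 identifies the subjects left out of PPS2 and PPS3 through the deviations listed in Appendix 4. SAP 7.1 (definition 11) and 11.3 (item 3) define ERIPD with reference to Appendix 4 for the details. For PPS the route differs: SAP 8.3 points to 11.3, and 11.3 leaves the definition of an important deviation to the Protocol Deviation Guidance. The last version of that Guidance approved before lock also defines the per-protocol sets in general.

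**The concern.** The SAP and its stated source give different limits under the same criterion numbers. A subject with a BMI of 40, for example, satisfies both BMI criteria of Amendment 3 and falls squarely within both Appendix 4 rows.

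The per-protocol analyses and the ERIPD analyses exist to show whether real departures from the protocol influence the comparison. The SAP justifies PPS, PPS2 and PPS3 on the ground that deviating subjects could pull the two arms together artificially. That check works only if the flags mark real deviations. If a limit wider than 19 to 35 applied when some subjects enrolled, literal use of the rows would remove eligible subjects and label them as eligibility violators. If 19 to 35 was the limit that applied, a reader holding Amendment 3 and the SAP has no way to see that.

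**Working it through.** No figure in the plan depends on these rows, so the check is a comparison of texts, a date calculation and a count of the analyses reached.

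**1. The limits side by side**

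| BMI (kg/m²) | Amendment 3 BMI criteria | Appendix 4 rows read literally |
|---|---|---|
| below 19 | met | important deviation |
| 19 to 35 | met | none |
| above 35, up to 45 | met | important deviation |
| above 45 | not met | important deviation |

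The documents disagree in the first and third bands. This is unlikely to be a text-extraction fault: both limits differ, and the range stands in two separate rows. Other Appendix 4 rows do match Amendment 3: age 18 to 75, HbA1c 7.0 to 11.0% for subjects on basal insulin, 12 weeks on at least two other antidiabetes medications, and 6 months on insulin.

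**2. Is there a version rule?** Four places come close.
- The Appendix 4 headers speak of deviations from the criteria, and SAP 11.3 item 3 of violating them. Neither names a version.
- SAP 11.3 fixes which version of the Guidance applies, not which version of the protocol.
- SAP section 11 mentions subjects treated under a previous protocol version, but only for data after Week 26.
- Protocol 15.2 requires IRB/IEC approval before a change is implemented, apart from immediate hazards and logistical or administrative changes. This implies that conduct follows the approved version. It is not a rule for coding deviations.

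**3. Could an earlier version have applied?** Amendment 3 is dated 25 April 2019. SAP 10.3 gives 13 August 2019 as the date of last patient follow-up. Both completer definitions in SAP 7.1 cover subjects "who received IP for at least 22 weeks".
- 25 April to 13 August 2019: 5 + 31 + 30 + 31 + 13 = 110 days.
- 22 weeks × 7 = 154 days, which is more than 110.
- Counting the first dose as Study Day 1, the latest first dose that allows 154 days by 13 August 2019 is 153 days earlier, 13 March 2019. That is 43 days before Amendment 3.
- If 13 August was instead the 30-day follow-up call, the date becomes 11 February 2019, 73 days before.

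Every 22-week completer therefore started treatment before Amendment 3 was dated. Neither document gives the BMI limit of any earlier version.

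**4. Analyses reached**

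| | Through Appendix 4 | Only if the Guidance has the same limits | Not reached |
|---|---|---|---|
| Primary-endpoint sensitivity analyses (5) | PPS2, ERIPD interaction | PPS | composite, completers |
| HbA1c analyses in SAP Table 5 (8) | no. 4 (PPS3), no. 6 (ERIPD interaction), one of six subgroups in no. 7 | no. 2 (PPS) | nos. 1, 3, 5, 8 |

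That is 2 of 5 directly, or 3 of 5 with PPS, and 3 of 8 directly, or 4 of 8 with PPS. The safety summaries and interaction models by ERIPD in SAP 11.8.1 also use the flag. The primary analysis uses the Safety Analysis Set and the main HbA1c analysis uses the FAS, so neither depends on the rows.

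**The case against.** The strongest reply is that the rows are labels for deviations, not a filter run on BMI values. Deviations are entered in the trial management system under the Guidance. The study team and sponsor review them without regard to treatment, and the per-protocol sets are finalized before lock. Given the headers and the ERIPD wording, a subject who met the criterion that applied has nothing to enter, and Protocol 15.2 makes the approved version the natural default. The dates point the same way: Amendment 3 did not yet exist when any 22-week completer started, so its BMI limit may be the wrong comparator for them.

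Much of this stands. It is a sensible reading, and it means that actual miscoding cannot be presumed. It does not close the gap, because the rows themselves state 19 and 35, no text ties them to a version, and the Guidance that might do so is not available.

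A second reply also stands: PPS membership rests on the Guidance. The Yes entries in Appendix 4 might lead a reader to infer that PPS is affected as surely as PPS2 and PPS3, but SAP 8.3 and 11.3 do not support that.

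Third, the silence of SAP 3.1 is weak evidence. The section records changes of statistical method, and a deviation code would not necessarily appear there.

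**Conclusion.** The mismatch is certain and sits in current, operative text. Applied literally, the two rows would take subjects who meet the Amendment 3 criterion out of PPS2 and PPS3 and flag them as ERIPD. For PPS this holds only on the assumption that the Guidance carries the same limits.

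A reader might infer that subjects have been misclassified, or that the per-protocol results are biased or underpowered. The documents do not support this. They give no BMI distribution, no count of flagged subjects and no earlier BMI limit. Harm requires that a limit wider than 19 to 35 applied while subjects outside that range enrolled, and nothing supplied shows this. I therefore give no estimate of bias or lost power. A reader might also infer a threat to the equivalence conclusions, but the primary analysis, the main HbA1c analysis and the hierarchical test between them do not use these flags.

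Severity is minor to should-fix. I take no view on which BMI limit is right.

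**What to change.** Before database lock:

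1. Reconcile the two Appendix 4 rows and the Protocol Deviation Guidance with the protocol.
2. Add a sentence to SAP 11.3 stating which protocol version governs eligibility deviations, for example the version approved and in force at the subject's enrolment. List the BMI limit by version.
3. Re-derive PPS, PPS2, PPS3 and the ERIPD flag accordingly.
4. Report by arm the number of subjects flagged on BMI alone, so that the practical effect is visible.

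The cost is two table rows, one sentence with a short list of limits, alignment of the Guidance and a rerun of the flags. The small downside is that the version in force, including site approval dates, must be checked for each BMI-flagged subject. SAP 11.3 already requires the per-protocol sets to be settled before lock, so the work fits an existing step.
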